component of TRAP is the causal agent. For example, Mills et al (Mills et al., 2011) reported that diesel exhaust exposure impaired vascular function but that filtered diesel exhaust (that retained its gaseous components) or pure carbon nano-PM did not. Similarly, Cosselman et al (Cosselman et al., 2012) reported a rapid increase in systolic BP (SBP; peaking 30–60 minutes from the start of exposure) but not diastolic BP (DBP) or heart rate (HR), upon exposure to diesel exhaust. In contrast, studies of the effects of short-term exposures to gaseous components of TRAP mixtures on cardiovascular function and BP are scarce. In the few studies we were able to find, the associations with adverse effects for O3 exposure are mixed (Li, 2018), while current evidence does not support an adverse acute effect of NO2 on vascular function (Langrish et al., 2010).

There have been over 90 studies assessing short-term effects of ambient ultrafine particles (UFPs; particles with aerodynamic diameter <100 nm and a component of TRAP) on cardiovascular indicators and outcomes (Ohlwein et al., 2019). There are also a growing number of long-term studies of UFP and health, with a particular focus on residential proximity to roadways, but these studies have reported mixed findings in terms of associations with cardiovascular health (Aguilera et al., 2016; Lane et al., 2016). Relatively few have studied short-term effects of TRAP, or its specific components such as soot (or black carbon [BC]) and UFP, on BP (Magalhaes et al., 2018).

It is difficult to draw causal relationships between TRAP and BP because of the observational nature of epidemiological studies, which include uncontrolled confounders, such as noise (Aguilera et al., 2016; Brauner et al., 2008; Brugge & Goble,

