2002; Lane et al., 2016; Magalhaes et al., 2018; Morishita et al., 2018; Ohlwein et al., 2019) and exposures are often estimated based on central-site measurements, which introduces exposure error. Controlled exposure studies offer the potential to test associations under highly scripted and characterized conditions. However, studies with exposure concentrations that are realistically encountered proximate to highways are lacking. Furthermore, evaluation of the effectiveness of strategies to mitigate TRAP exposures, such as use of commercially available, stand-alone HEPA filtration, have, to date, shown limited benefits on BP and peripheral blood inflammation (Brauner et al., 2008; Brugge & Goble, 2002; Morishita et al., 2018). Morishita et al (Morishita et al., 2018) found reductions in SBP in older adults living in an urban area with 3-day use of HEPA filtration, which also reduced indoor PM2.5, but PM2.5 is not a marker of TRAP emissions. Therefore, the aim of our study was to assess whether reducing TRAP exposure by limiting indoor infiltration and deploying HEPA filtration for a short duration could have a beneficial effect on BP.

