## **Air Quality and Outcome Measures and Exposure Room Configuration**

### **Air Quality Measurements**

Particle number concentrations (PNC) and black carbon (BC) concentrations were monitored continuously. PNC was measured using a water-based condensation particle counter (TSI, Inc; model 3873;  $d_{50}=7$  nm) at 1-second resolution and BC concentration was measured with an aethalometer (Magee Scientific; model AE16) at 1-minute resolution. For the first half of the sessions, temperature was measured centrally in the room, and for the latter half of the sessions, temperature was measured directly adjacent to each study participant with a temperature logger (Onset Computer Corporation; model HOBO UX100-003).

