### **Exposure Room Configuration**

Exposure sessions were held at 2 near-highway locations (shown in Figure S1) where ambient air was enriched in TRAP. Most of the participants (n=63) attended exposure sessions in a ground-floor community room of a low-income housing development located near the intersection of I-90 and I-93 (average weekday daily traffic, 240 000 vehicles/day) in Chinatown, Boston. For the other 14 participants, sessions were conducted at another community room (on the ground floor in a multistory building) located in Somerville, MA, which was adjacent to I-93 and R38 (average weekday daily

traffic, 215 000 vehicles/day). Sessions were conducted in the morning (during 06:00–09:00 hours) to coincide with rush-hour traffic and lower atmospheric dispersion, that is, when TRAP concentrations were expected to be the highest (verified by diurnal trends measured at a vicinal near-highway regulatory monitoring site [ID: 25-025-0044]).

Three levels of exposure—low, medium, and high—were attained by varying the degree of ventilation (and thereby infiltration) and by increasing or decreasing the number or blower setting of HEPA filtration units. Two brands of HEPA air filters were used at both locations: IQ Air Health Pro (1 unit) and Austin Air Healthmate 400 (up to 7 units with 4-stage filter, which also contained granular activated carbon and zeolite).

Based on air quality measurements before the exposure sessions, we determined that a concentration of ≈20 000 to 30 000 particles/cm^3 could be expected during the high-exposure sessions and 10-fold lower concentrations could be attained in the low-exposure sessions. We targeted 33–50% lower than high-exposure concentrations, that is, 10 000 particles/cm^3, for the medium-exposure sessions.

During low exposure, infiltration of outdoor air into the room was minimized by closing doors and sealing the cracks underneath with duct tape. Neither exposure room had operable windows. Filtration of TRAP was maximized by continually running air filters (4 units at the Somerville location and 8 units at the larger Chinatown location).

During medium exposure, infiltration was restricted by closing doors, but cracks underneath were left unsealed. Filtration was optimized to maintain indoor PNC in the 8000- to 12 000-particles/cm^3 range by using 0 to 4 air filters.

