During high exposure, infiltration was maximized by cross-ventilating the rooms by partially opening the doors that connected the room directly to outdoors and in the Somerville location, by adding a fan in addition to door opening (since cross-ventilation was not an option in that room). Air filters were not used during high exposures.

Both community rooms were located within a block of restaurants, which resulted in a noticeable odor during the last 30 to 45 minutes of some sessions when restaurants began cooking. Odor was only perceivable in some of the high-exposure sessions because this configuration allowed odors into the rooms.

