### **Statistical Analysis Plan:**

A linear mixed model was used to analyze the 3-exposure, 3-period crossover design. The primary outcome measure is the change in systolic blood pressure from the beginning of each exposure session. Before calculating change scores in each exposure session, each participant's systolic blood pressure measurements was smoothed using a 3-time-period, centered moving average. A random intercept was included in the linear mixed model to account for the interdependence of the observations that arise by each participant attending each exposure session. In addition, the model included baseline systolic blood pressure, mean room temperature for each session, and 2 time-varying covariates, particle number count and black carbon concentrations. A Toeplitz covariance structure was used to characterize the interdependence of the observations over time. Period and carryover effects was assessed in the linear mixed model. The mean dose-response effect of filtration was assessed for statistical significance using a linear contrast. An identical approach was

used to analyze diastolic blood pressure and heart rate. Particle number count and black carbon concentrations was also analyzed using a linear mixed model with average room temperature as a fixed covariate and a Toeplitz covariance structure.

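### The blood pressure model adjusts for particle number and black carbon measured during the session, so the filtration contrast is not the total effect of reducing TRAP

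*Combined protocol and SAP*

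**What the plan says.** The last sentence of the Objective section gives the aim, which is to "assess whether reducing TRAP exposure by limiting indoor infiltration and deploying HEPA filtration for a short duration could have a beneficial effect on BP". That is a question about the total effect of the assigned condition.

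The Statistical Analysis Plan describes one linear mixed model for change in systolic pressure. Its listed terms are a random participant intercept, baseline systolic pressure, mean room temperature and "2 time-varying covariates, particle number count and black carbon concentrations", with a Toeplitz covariance; period and carryover are also assessed. Exposure condition is not listed. The test of the intervention follows directly: "The mean dose-response effect of filtration was assessed for statistical significance using a linear contrast". Diastolic pressure and heart rate are handled in the same way. The section closes with a separate analysis: "Particle number count and black carbon concentrations was also analyzed using a linear mixed model".

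Under Exposure Room Configuration, the three conditions are made by changing ventilation and filtration with PNC levels in view. For the medium condition, "Filtration was optimized to maintain indoor PNC in the" range of 8000 to 12 000 particles/cm³.

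**The concern.** PNC and BC are recorded continuously during the session, so they are measured after assignment and are altered by it. They also index the mechanism under study: the Objective section cites evidence that the particulate "component of TRAP is the causal agent", and it names BC and ultrafine particles as components of TRAP. A contrast between conditions that is adjusted for them compares room configurations as if PNC and BC were equal. What is left is any effect through other routes.

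The primary test is therefore weakened to the extent that the protocol's own mechanism is correct. A null result would not tell the reader whether filtration lowers blood pressure. A positive result could be credited to fewer particles when it reflects something else about the rooms. The same applies to diastolic pressure and heart rate.

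**Working it through.** The documents contain no sample size calculation, target effect, blood pressure SD, or PNC or BC variance. There is no planned figure to reproduce. The direction follows from the text; the size is illustrated under stated assumptions.

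**1. Where PNC and BC sit.** Condition sets ventilation and filtration, which set PNC and BC, which are proposed to affect blood pressure. The plan models PNC and BC as responses in one analysis and as covariates in another. The linear contrast implies that condition is in the blood pressure model. If it were not, that model would contain no filtration contrast.

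**2. What the adjusted contrast targets.** Write the high-minus-low total effect as τ = δ + β·ΔPNC, where δ is the effect by other routes. A model with condition and PNC estimates δ. If a share *s* of τ runs linearly through current PNC, the adjusted contrast is (1 − *s*)·τ.

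- Exposure Room Configuration gives about 20 000–30 000/cm³ for high, with low 10-fold lower. Taking 25 000 and 2500, ΔPNC = 22.5 thousand/cm³.
- Assume τ = 3 mmHg. With *s* = 1, β = 3/22.5 = 0.133 mmHg per thousand/cm³.
- The adjusted contrast is then 0, 0.75, 1.5, 2.25 and 3.0 mmHg for *s* = 100%, 75%, 50%, 25% and 0%.

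**3. Check on session means.** From the documents: 63 + 14 = 77 participants and 24 sessions of each type. Assumed: PNC centres 2.5, 10 and 25 thousand/cm³, between-session log-SD of PNC 0.3, session-level residual SD 6 mmHg, 400 runs. The regression is within participant.

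| Share through PNC | Without PNC/BC | With PNC/BC |
|---|---|---|
| 100% | 3.10 | −0.21 |
| 75% | 3.13 | 0.71 |
| 50% | 3.26 | 1.99 |
| 25% | 3.03 | 2.37 |
| 0% | 3.02 | 3.19 |

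The Monte Carlo error of an adjusted mean is about 2.77/√400 = 0.14, and the 1.99 is a chance excess. Repeating with 4000 runs gives 0.06, 0.82, 1.54, 2.31 and 3.04, which agrees with step 2. The standard error rises from 0.98 to about 2.8, a variance ratio of (2.77/0.98)² ≈ 8. For log-SD 0.5 and 0.15 the ratios are (1.83/0.98)² ≈ 3.5 and (5.25/0.98)² ≈ 29.

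**4. Check on repeated readings.** There are 120/10 = 12 readings per session after the start. The fitted model has condition, period, time, baseline and temperature, a participant intercept and an estimated Toeplitz covariance. Readings are smoothed with the 3-point average. Assumed: τ = 3 mmHg, between-participant-session SD 5 mmHg, PNC CV 0.2–0.5 between and 0.05–0.5 within sessions, 400 runs per setting. Without PNC and BC the estimate is 3.0 mmHg and rejection 91–93%. With them:

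| Mechanism | Estimate, mmHg | Rejection |
|---|---|---|
| Wholly through current PNC | 0.0–0.1 | 7–9% |
| Half through current PNC | 1.5–1.6 | 24–40% |
| Through cumulative PNC | 1.3–2.6 | 24–82% |
| Not through PNC | 3.0–3.1 | 56–92% |

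Variance inflation here is 1.0–2.9, and 2.7–9.7 if PNC hardly varies within a session (CV 0.01). It is lower than in step 3 because session means discard the within-session variation that separates PNC from condition. A second set of assumed variances (150 runs per cell, covariance treated as known, no baseline or temperature term) gives 0.4–2.4 mmHg for the cumulative mechanism and inflation of 1.1–6.4. Carryover was not simulated.

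**The case against.** **Parameterisation.** The plan does not say how PNC and BC enter. If both were centred within condition, the contrast would stay at the total effect; the session-mean check then gives 3.0–3.1 mmHg with a standard error of about 1.0. That is correct, but no such centring is stated, and raw time-varying covariates are the natural reading.

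**The adjusted contrast may mean something.** It is not empty by construction. Some filters contain carbon and zeolite, and odor differs by condition: "Odor was only perceivable in some of the high-exposure sessions because this configuration allowed odors into the rooms". It is still not the effect named in the aim. Nor is it a clean direct effect, because PNC varies within a condition for non-randomised reasons. The planned PNC ranges (about 2000–3000, 8000–12 000 and 20 000–30 000) also do not overlap, so equality across conditions rests largely on linear extrapolation.

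**The particle mechanism is uncertain.** The protocol offers it as evidence, not as established. It defines TRAP as gases plus particles, and it reports that pure carbon nanoparticles did not impair vascular function. Complete loss of the effect is therefore an extreme case. This limits the size of the problem, not its existence.

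**The figures are soft.** One effect size was used, with a single blood pressure SD in each check. In the wholly-through-PNC case a 5% test rejected 7–9% of the time, against a Monte Carlo error of √(0.05 × 0.95/400) ≈ 1.1 points, so the rejection rates in step 4 run slightly high. The estimates, not the rejection rates, carry the argument.

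**Conclusion.** The point holds, and the plan is wrong as written. The only blood pressure model described conditions on two consequences of the intervention that lie on its intended pathway. Its filtration contrast does not estimate the total effect of reducing TRAP. This rests on two readings of the text: that condition is in the same model, which the contrast implies, and that PNC and BC are not centred within condition, which the plan does not mention.

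The size cannot be derived from the documents. For an assumed 3 mmHg effect, the loss ranges from none, if particles play no part, to all of it, if the effect follows current PNC. Loss of precision is a further risk, from negligible to large, depending mainly on how steady PNC was within sessions. The adjusted contrast matches the total effect only where particles do not matter, which runs against the protocol's rationale.

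**What to change.** For systolic pressure, diastolic pressure and heart rate, take the linear contrast from a model that names exposure condition explicitly. Include period, carryover as already assessed, the baseline value and mean room temperature, with any time-in-session term, the participant intercept and the Toeplitz covariance, but without PNC and BC.

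Temperature needs its own check. It is recorded during the session, open or sealed doors may affect it, and the method changed part-way ("For the first half of the sessions, temperature was measured centrally in the room", and beside each participant later). Report the contrast without it as a sensitivity analysis.

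Use measured PNC, and separately BC, in a secondary exposure-response model where it replaces condition, or in an analysis labelled as mediation. If the adjusted contrast is also kept, describe it as an effect at fixed PNC and BC.

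The cost is revised wording and model runs on existing data: three primary contrasts, a temperature sensitivity run and a secondary exposure-response model. Done for every outcome, with PNC and BC modelled separately, that is 3 + 3 + 6 = 12 runs. No new data are needed. Because the plan is written in the past tense, label the re-run as a revised analysis and show it beside the adjusted one.
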